2.1.1. Calculation of Conditional Power

At the interim, the conditional power for the current trend and the hypothesized trend will be calculated (Lan KKG, 1988). The conditional power will be presented for the comparison of each dose regimen to the placebo.

Then Conditional Power at time *t* is given by:

Conditional Power =
$$\Phi[Z_{CP}]$$
,

where Φ is the standard normal cumulative distribution function and

Current Trend:
$$Z_{CP}(t) = \frac{Z_t}{\sqrt{t}} - Z_{\alpha/2}$$
 at t=0.5 and $\alpha = 0.10$

$$\text{Hypothesized (H1) trend: } Z_{CP}(t) = \frac{\left(Z_t * \sqrt{t}\right) + (1-t)*\left(Z_{\alpha/2} + Z_{\beta}\right) - Z_{\alpha/2}}{\sqrt{1-t}}$$

at t=0.5 and
$$\alpha = 0.10$$
, $\beta = 0.150$

Version 2.0

The statistic Z_t will be calculated as $Z_t = (LS Mean Difference)/Standard Error, with these values obtained from the SAS statistical output.$

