# 9.6.1.8 Interim Analysis

An interim analysis of the primary efficacy endpoint will be conducted using unblinded data after

This analysis will have 2 potential outcomes:

- If neither dose regimen of fipaxalparant (HZN-825) shows better efficacy compared to placebo with an acceptable safety profile, the trial will be discontinued for futility.
- If 1 or both dose regimens of fipaxalparant (HZN-825) show better efficacy compared to placebo with an acceptable safety profile, the trial will continue with no changes.

Fipaxalparant (HZN-825)

Version 5.0, Amendment 4

Protocol: HZNP-HZN-825-303

Fipaxalparant (HZN-825) Protocol: HZNP-HZN-825-303 Version 5.0, Amendment 4

The futility analysis will not be used to make a positive determination of efficacy to stop the trial.

Conditional power will be used to determine which of the options is chosen, with a conditional power of  $\geq 10\%$  required for at least 1 dose regimen to continue the trial. Other statistics, such as Bayesian statistics, may also be used for the futility analysis and dose selection.

To support the dose selection and as part of the Week 28 unblinded interim analysis, the FVC % predicted change from Baseline at Week 28 will be evaluated in subjects who were randomized with concomitant standard-of-care treatment at Baseline. Approximately 60 subjects in the standard-of-care stratum with 28 weeks of data (approximately 20 subjects per arm) will be included. The positive signal in the FVC % predicted change from Baseline at Week 28 and related results in standard-of-care subjects will support the dose selection and future trial design.

Additionally, safety will be assessed, and an fipaxalparant (HZN-825) dose regimen that has an unacceptable safety profile will be discontinued and subjects assigned to that dose regimen would be assigned to the other dose regimen for the remainder of the trial, if the other dose regimen continues.

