1.3. Sample Size and Power

Approximately 135 subjects (45 subjects per treatment group) will be enrolled in the trial. Based on a prior trial of pirfenidone [Nathan et al., 2019] in a similar subject population, change in FVC % predicted is expected to have a standard deviation of 6% to 9% after 52 weeks of treatment. Assuming a clinically important difference between HZN-825 and placebo is 3% and a common standard deviation is 9%, a sample size of 45 subjects per treatment group in the Core Phase will provide 85% probability to detect a positive signal (FVC % predicted difference for each dose vs. placebo at Week 52 >1%) and 70% probability to detect a positive signal (FVC % predicted difference for each dose vs. placebo at Week 52 >2%). If the true FVC % predicted difference for each dose versus placebo at Week 52 is 0%, then there is only 15% probability to detect a positive signal (FVC % predicted difference for each dose vs. placebo at Week 52 is 0%, then there is only 15% probability to detect a positive signal (FVC % predicted difference for each dose vs. placebo at Week 52 >2%).

The sample size for the Extension Phase is based on the number of subjects who complete the Core Phase.

[figure not shown]
Version 2.0

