2. TYPE OF PLANNED ANALYSIS

2.1. Interim Analysis

An external multidisciplinary IDMC will review the progress of the trial and perform interim reviews of the study data in order to protect subject welfare and preserve trial integrity. The IDMC will include at least 1 statistician and at least 2 clinicians experienced in clinical trials and the therapeutic area. IDMC review will be conducted according to the timelines outlined in the IDMC charter.

A futility analysis for dose selection will be conducted at the interim analysis

The IDMC will recommend stopping the study for a conclusion of futility if the conditional power for both doses is less than 10% The IDMC may recommend stopping only one posology only if there is a clear safety signal that precludes continuation of one posology. Unless this occurs, the IDMC will either recommend continuing both posologies or stopping both posologies in this study.

If the IDMC recommends continuing the study, the IDMC will further recommend which of the two posologies will be used for investigation in future trials of HZN-825. The IDMC members will use the following decision criteria in making this recommendation:

- If one of the two posologies has a clear safety signal that precludes further study, the other posology will be recommended.
- If only one of the two posologies has a conditional power of at least 10% without additional safety signals then that posology will be recommended.
- 3 Similarly, if one of the two posologies has a conditional power that exceeds that of the other posology by at least 10 percentage points, without additional safety signals, the posology with the higher conditional power will be recommended.
- 4 If both posologies have similar conditional power and no unique safety signals appear with either posology, the IDMC is expected to recommend the lower dose.

To support the dose selection, and as part of the Week 28 unblinded interim analysis the FVC % predicted change from Baseline at Week 28 may be evaluated in full analysis set (FAS) subjects with concomitant treatment of standard of care at the baseline. The positive signal in the FVC % predicted change from Baseline at Week 28 and related results in subjects with standard of care will support the dose selection and future trial design.

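### SAP 2.1.1 prints current-trend conditional power without its √(1−t) divisor, so a printed 10% is a true 3.5%; the hypothesised trend rests on an effect the SAP does not state

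*SAP*

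**What the plan says.** SAP 2.1.1 cites the B-value method and sets out two calculations: "At the interim, the conditional power for the current trend and the hypothesized trend will be calculated". Each is Φ(Z_CP), for each dose against placebo, with Z_t the LS mean difference over its standard error.

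- Current trend: "Z_{CP}(t) = \frac{Z_t}{\sqrt{t}} - Z_{\alpha/2"}, at t = 0.5 and α = 0.10. Nothing is divided by √(1−t).
- Hypothesised trend: [Z_t√t + (1−t)(Z_{α/2} + Z_β) − Z_{α/2}] / √(1−t), at t = 0.5, α = 0.10 and β = 0.150.

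SAP 2.1 attaches the decisions. On futility: "The IDMC will recommend stopping the study for a conclusion of futility if the conditional power for both doses is less than 10"%. If the trial continues, the regimen recommended for future trials depends on the same 10% mark, and then on a gap: "if one of the two posologies has a conditional power that exceeds that of the other posology by at least 10 percentage points". Protocol 9.6.1.8 agrees ("Conditional power will be used to determine which of the options is chosen") and adds: "Other statistics, such as Bayesian statistics, may also be used for the futility analysis and dose selection".

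SAP 1.3 plans on a 3-point difference and an SD of 9, from a change "expected to have a standard deviation of 6% to 9% after 52 weeks of treatment". Its only 85% figure is this: "a sample size of 45 subjects per treatment group in the Core Phase will provide 85% probability to detect a positive signal", where a positive signal means an observed difference above 1 point.

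**The concern.** Two separate points arise, and only one of them can reach the 10% rule.

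**Formula.** Both lines carry the same label and should differ only in the drift assumed for the rest of the trial. The current-trend line lacks a divisor that its neighbour has. Below 50%, leaving it out overstates conditional power, so a 10% futility cut becomes more lenient than it reads. The committee could continue at a true conditional power as low as 3.5%, and both the 10% pass mark and the 10-point gap for choosing a regimen would be read on the wrong scale.

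**Input.** The hypothesised-trend formula is correct. However, β = 0.150 fixes the alternative at 85% power for the two-sided 0.10 test, and the SAP does not say which difference and SD that represents. The 3-point design in SAP 1.3 does not have 85% power at either end of its SD range. This is an unstated assumption, not an arithmetic error.

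**Working it through.** **Inputs.** α = 0.10 two-sided (Z_{α/2} = 1.6449); t = 0.5; β = 0.150 (Z_β = 1.0364), all from SAP 2.1.1. From SAP 1.3: 45 per arm, 3 points, SD 6 to 9. The two dose comparisons share one placebo group of equal size, so their statistics have correlation 0.5.

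**1. Reproduce SAP 1.3.** SE = 9√(2/45) = 1.897. Φ((3−1)/1.897) = 85.4%; Φ((3−2)/1.897) = 70.1%; Φ((0−2)/1.897) = 14.6%. The stated 85%, 70% and 15% all reproduce. The 85% is the chance of seeing more than 1 point, not the power of the test.

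**2. Derive the current-trend line from the SAP's own formula.** Put the observed drift Z_t/√t in place of Z_{α/2} + Z_β in the hypothesised-trend line. The numerator becomes Z_t√t + (1−t)Z_t/√t − Z_{α/2} = Z_t/√t − Z_{α/2}. The divisor stays:

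Z_CP = (Z_t/√t − Z_{α/2}) / √(1−t).

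Consistency check: when the observed drift equals 1.6449 + 1.0364 = 2.681, the two trends are the same assumption and must agree. As printed they give Φ(1.036) = 85.0% and Φ(1.036/0.7071) = 92.9%.

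**3. Size at the cut.** Φ⁻¹(0.10) = −1.2816.

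- A printed 10% is truly Φ(−1.2816/0.7071) = 3.5% (simulation with 4 million draws: 3.5%). A true 10% prints as Φ(−1.2816 × 0.7071) = 18.2%.
- Z_t cut as printed: (1.6449 − 1.2816) × 0.7071 = 0.257. Correct: (1.6449 − 1.2816 × 0.7071) × 0.7071 = 0.522.
- As an observed difference, taking interim SE = final SE/√0.5 (2.683 at SD 9, 1.789 at SD 6): 0.69 against 1.40 points at SD 9, and 0.46 against 0.93 at SD 6.

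**4. The hypothesised trend.** Final SE is 1.265 (SD 6) or 1.897 (SD 9).

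- Three points give drift 3/1.265 = 2.37, with power Φ(2.37 − 1.645) = 77% at SD 6; and 3/1.897 = 1.58, with power 47% at SD 9.
- Drift 2.681 corresponds to 2.681 × 1.265 = 3.39 points at SD 6, or 2.681 × 1.897 = 5.09 points at SD 9.
- The 10% cut on Z_t is (−1.2816√(1−t) + 1.6449 − (1−t) × drift)/√t: −0.851 for drift 2.681, −0.632 for 2.37 and −0.073 for 1.58.

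**5. Probability of stopping** (both statistics below the cut, bivariate normal, correlation 0.5):

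| Rule | No effect in either dose | 3 points in both, SD 9 | 3 points in both, SD 6 |
|---|---|---|---|
| Current trend, as printed | 44% | 8.4% | 2.3% |
| Current trend, with divisor | 56% | 13.9% | 4.4% |
| Hypothesised, β = 0.150 | 8.5% | 0.45% | 0.06% |
| Hypothesised, 3-point drift at SD 9 | 30% | 4.0% | – |
| Hypothesised, 3-point drift at SD 6 | 13% | – | 0.14% |

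**6. Dose recommendation.** Take Z_t = 0.55 and 0.30. As printed they give 19% and 11%: both pass, and the 8-point gap counts as similar. Corrected they give 11% and 4%: only one passes. Such cases are uncommon. In simulation, among trials that continue under both versions, the recommendation differs in about 1% to 4%. This applied the SAP 2.1 criteria in order, with no safety signal and a gap under 10 points read as similar.

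**The case against.** The governing trend may be named in text that cannot be seen. The stopping sentence in SAP 2.1 breaks off after its threshold, and redacted words are not missing from the plan. This stands: no effect on the 10% rule is established, and each consequence above is conditional on the trend used.

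The equation was read from a PDF by a program, so a divisor could have been lost. That is possible, though the neighbouring equation kept its own.

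The strongest point is that, at the only t the SAP uses, the printed expression is a coherent statistic. Flat-prior predictive power is Φ[(Z_t/√t − Z_{α/2})√(t/(1−t))], and the last factor equals 1 at t = 0.5. The Protocol permits Bayesian statistics, and where to place a futility cut is the sponsor's choice. This means the defect may be the label and not the rule. It does not remove the mismatch: the SAP calls the quantity conditional power and cites the B-value method, and the Protocol lists Bayesian statistics as additional to conditional power.

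On β = 0.150, defining the alternative by a standardised drift is legitimate, and nothing in the SAP says that it represents 3 points. At SD 6 the implied 3.4 is close to 3, and the two match exactly at SD 3/(2.681 × √(2/45)) = 5.3. This half is therefore a request for clarification.

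**Conclusion.** The concern holds. As printed, the current-trend line is not conditional power: it contradicts the hypothesised-trend line beside it and reads 10% where the true value is 3.5%. If that trend governs, the chance of stopping an ineffective trial falls from 56% to 44%, so about 11.5% of such trials continue only because of the missing divisor. The effect on dose recommendation is small.

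If the hypothesised trend governs, the formula is sound but the 10% is measured against an unstated effect larger than 3 points. The chance of stopping with no effect is then 8.5%, against 13% (SD 6, a modest gap) or 30% (SD 9, a large one) for the stated 3 points.

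The difference-scale figures and implied effects assume 45 evaluable subjects per arm, no covariate adjustment, and interim information equal to half the final Week 52 information. The interim sample and timing are not visible. Confidence is moderate because of the possible redaction and the machine-read equation. This should be fixed, but it does not threaten type I error.

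**What to change.** In SAP 2.1.1:

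1. Check the source page for a lost divisor. If it is absent, print the current trend as Z_CP(t) = (Z_t/√t − Z_{α/2})/√(1−t). Alternatively, keep the quantity, call it predictive power with a flat prior, show the factor √(t/(1−t)), and state that its 10% cut equals about 3.5% conditional power.
2. State the difference and SD that define the hypothesised trend and use the drift they imply (1.58 for 3 points at SD 9, 2.37 at SD 6). Or keep β = 0.150 and state that it represents 3.4 points at SD 6 or 5.1 at SD 9.
3. If the unredacted SAP 2.1 does not already do so, name the trend compared with 10%.

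The cost is SAP wording and one line of code, plus the IDMC charter if it repeats the formula (the charter was not available). The stricter options raise wrongful stopping when both doses truly give 3 points. For the corrected current trend it goes from 8% to 14% at SD 9 and from 2.3% to 4.4% at SD 6. For the 3-point hypothesised drift it goes from about 0.4% to 4.0% at SD 9 and from 0.06% to 0.14% at SD 6. A sponsor who prefers the looser boundary can keep it by relabelling or by stating the alternative, with no added wrongful stopping.

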# 9.6 Statistical Methods and Determination of Sample Size

# 9.6.1 Core Phase

### **9.6.1.1 Endpoints**

# 9.6.1.1.1 Primary Efficacy Endpoint

The primary endpoint is the change in FVC % predicted from Baseline to Week 52.

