3. GENERAL CONSIDERATIONS FOR DATA ANALYSES

Categorical variables will have the number and percentage of subjects in each category presented; for continuous variables, the number of subjects (n), mean, standard deviation (SD) or standard error (SE), median, first quartile (Q1), third quartile (Q3), minimum, and maximum will be presented.

All statistical tests will be 2-sided and performed at the 10% significance level unless otherwise specified.

For additional details on data presentation, refer to the tables, listings, and figures (TLF) document.

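### SAP 2.1.1 fixes the information fraction at t = 0.5 and does not name the visit behind the interim Z, although a Week 52 endpoint is tested at a look labelled Week 28

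*SAP*

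**What the plan says.** - **Endpoint.** Protocol 9.6.1.1.1: "The primary endpoint is the change in FVC % predicted from Baseline to Week 52". Protocol 9.6.1.8 applies the look to that endpoint: "An interim analysis of the primary efficacy endpoint will be conducted using unblinded data after" (the rest of the sentence is redacted).
- **Label.** SAP 2.1 describes a subgroup evaluation carried out "as part of the Week 28 unblinded interim analysis". Protocol 9.6.1.8 uses the same label and counts its standard-of-care subset by 28 weeks of data.
- **Formulas.** SAP 2.1.1 says that "the conditional power for the current trend and the hypothesized trend will be calculated". Both lines are evaluated "at t=0.5 and $\alpha = 0.10", and the hypothesised-trend line adds beta = 0.150. SAP 3 makes the 10% level two-sided: "All statistical tests will be 2-sided and performed at the 10% significance level unless otherwise specified".
- **Interim statistic.** "The statistic Z_t will be calculated as $Z_t = (LS Mean Difference)/Standard Error". No visit is named, and the MMRM of SAP 6.1.1.1 gives one contrast per visit.
- **Use.** SAP 2.1 has the IDMC recommend stopping if conditional power is below 10% for both doses. A gap of at least 10 percentage points between doses selects the regimen for future trials.

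No readable text derives t = 0.5, says that it will be updated, or says which of the two trends the 10% rule uses.

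**The concern.** The hypothesised-trend formula splits the final statistic into √t·Z_t plus an independent remainder with mean (1−t)·drift and variance 1−t. That split is valid only when t is the fraction of the final information on the tested contrast that is already in hand. This is what t means in the B-value method that SAP 2.1.1 cites. Two readings of Z_t are possible.

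- **Week 52 contrast.** At a look defined by Week 28 follow-up, t depends on how many subjects have reached Week 52 and on how well earlier visits predict that value. It is an observed quantity, and nothing readable ties it to 0.5.
- **Week 28 contrast.** The interim and final statistics then concern different visits. Their correlation is √t times the Week 28–52 correlation, not √t, so the formula does not apply to the Week 52 test.

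If t is too high, the trial can be recommended for stopping while a dose still has a fair chance. If t is too low, it can continue with almost none. The dose-selection comparison inherits the same error.

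**Working it through.** **Inputs from the documents.** Alpha 0.10 two-sided gives z = 1.645. Beta 0.150 gives 1.036, so the printed drift is 1.645 + 1.036 = 2.681. SAP 1.3 gives a difference of 3, SD 9 and 45 per arm.

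**Assumptions.** Uniform accrual over A = 52 to 104 weeks, no dropout, and a Week 28–52 correlation ρ of 0.6 to 0.8. None of these is in the documents.

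**1. The plan's design figures.** SE = 9√(2/45) = 1.897. The probability that the observed difference exceeds 1 if the truth is 3 is 85.4%. Exceeding 2 if the truth is 3 is 70.1%, and exceeding 2 if the truth is 0 is 14.6%. These match the stated 85%, 70% and 15%. The design drift is therefore 3/1.897 = 1.581. The value t = 0.5 has no stated derivation to reproduce.

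**2. The printed hypothesised-trend boundary.** Conditional power is Φ[(Z√t + (1−t)·drift − 1.645)/√(1−t)]. Setting it to 10% at t = 0.5:

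Z = (−1.282×0.7071 − 0.5×2.681 + 1.645)/0.7071 = −0.851.

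**3. Information fraction for the Week 52 contrast.** If a share q of subjects has reached Week 28, the share with Week 52 is q − 24/A. With two visits, t = 1/[ρ²/q + (1−ρ²)/(q − 24/A)]. For q = 0.5:
- A = 52, ρ = 0.6: 1/(0.72 + 16.64) = 0.06.
- A = 104, ρ = 0.8: 1/(1.28 + 1.34) = 0.38.

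Using all five MMRM visits (generalised least squares, random slope plus noise, SD 9 at Week 52) raises these a little:

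| Share at Week 28 | Share with Week 52 | t, two visits | t, five visits |
|---|---|---|---|
| 50% | 4% to 27% | 0.06 to 0.38 | 0.09 to 0.45 |
| 75% | 29% to 52% | 0.37 to 0.65 | 0.44 to 0.71 |
| 100% | 54% to 77% | 0.65 to 0.90 | 0.71 to 0.93 |

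The lowest corner is 0.08 to 0.09, depending on rounding. There, only about 4% of 135 subjects (about five) have a Week 52 value.

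**4. What a stated 10% becomes on the hypothesised-trend line (Z = −0.851).**
- t = 0.09: (−0.255 + 2.440 − 1.645)/0.954 = 0.57, so 71%.
- t = 0.45: (−0.571 + 1.475 − 1.645)/0.742 = −1.00, so 16%.
- t = 0.44 to 0.71: about 18% down to 0.1%.
- t = 0.71 to 0.93: below 1%.

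With the design drift of 1.581 in place of 2.681, the same Z gives 2.0% at t = 0.5, 31% at t = 0.09 and 3.5% at t = 0.45.

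**5. Current-trend line.** The standard form is Φ[(Z/√t − 1.645)/√(1−t)]. Its 10% boundary at t = 0.5 is Z = 0.522, and that Z is 20% at t = 0.3 and 3% at t = 0.7. As the line reads in the SAP, the √(1−t) divisor is absent. Its boundary is then Z = 0.257, and a stated 10% moves only between about 8% (t = 0.93) and 23% (t = 0.08).

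**6. If Z_t is the Week 28 contrast in half the subjects.** Further assumptions are that the effect accrues linearly and that the Week 28 SD is 0.6 to 0.8 of the Week 52 SD. Then:
- drift₂₈ = √0.5·drift·(28/52)/(SD ratio).
- The final Z has conditional mean drift + ρ√0.5(Z − drift₂₈) and variance 1 − ρ²/2.

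A stated 10% is 31% to 56% at drift 2.681, and 9% to 21% at drift 1.581.

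**The case against.** **The trigger is redacted.** This is the strongest objection. The sentence that would justify 0.5 is blacked out in both documents, and redacted text cannot be counted as missing from the plan. A reader might infer that t = 0.5 is a wrong number and that the stopping rule is therefore misapplied. The documents do not support that. The value is exact if half the subjects have Week 52 data and no others contribute, and the 75% case straddles it. The label alone does not settle the matter, and 28/52 = 0.54 is calendar time, not information. This objection stands in full against any claim of demonstrated error.

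**The sizes depend on which line is used.** The large movements belong to the hypothesised-trend line at a drift of 2.681, which the stated design does not have. At 1.581 the half-subject range falls to 3.5% to 31%, which spans 10%. The printed current-trend line hardly moves. This also stands, and it is why both drifts and both lines are shown.

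**The consequence is limited.** The IDMC recommends, Protocol 9.6.1.8 allows other statistics such as Bayesian ones, and there is no efficacy stop, so type I error is unaffected. An unseen charter sets the scope of the IDMC's analyses. This is fair, but the 10% figure is still the stated criterion.

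**What remains.** A planned constant stands in for an observed quantity, and neither the visit nor the governing trend is stated. No trigger would remove that gap.

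**Conclusion.** This is a specification gap worth closing, not a proven error. With t fixed and no visit named for Z_t, the 10% rule and the 10-point dose comparison are not tied to the Week 52 information actually available.

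Under the assumed accrual, dropout and correlation, t could lie anywhere from about 0.09 to 0.93. A stated 10% on the hypothesised-trend line could then mean anything from well under 1% to about 71% at the printed drift. It also follows that the direction of any error is unknown: half the subjects at Week 28 puts t below 0.5, and all of them puts it above. A reader should not conclude that the trial would be stopped wrongly, or continued wrongly.

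Two further features of SAP 2.1.1 are separate: the missing √(1−t) in the current-trend line as read from the PDF, and a beta that implies a larger drift than the stated design. Correcting them would not settle t.

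**What to change.** In SAP 2.1.1:

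1. Replace the fixed t by the observed information fraction for each dose: t = (projected final SE / interim SE)², for the Week 52 MMRM contrast against placebo.
2. State that Z_t is that Week 52 contrast, and say which trend governs the 10% rule.
3. If Week 52 data are too sparse to fit the contrast, compute conditional power for the final Week 52 test from the joint normal distribution of the Week 28 and Week 52 statistics, using their estimated correlation.
4. Keep the 10% threshold.

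The cost is one SAP paragraph and a few lines of code for the unblinded interim statistician, with no extra data. If the observed fraction is 0.5, the information fraction in the formulas is unchanged. The small downside is that t is known only at the look.
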